5.3.1.1 Study Procedures

The study procedures outline in [Table 4](#) and [Table 5](#) are discussed in detail in this section, with the exception of the assessment of concomitant medications (Section [5.2.3.2](#)), the monitoring of treatment compliance (Section [5.5.6](#)), the collection of adverse event information (Section [6.4](#)), the collection of the IL28B sample (Section [5.3.1.3](#)), the collection of blood samples for the optional pharmacogenetic analysis (Section [5.3.1.3](#)), and the collection of blood samples for pharmacokinetic analysis (Section [5.3.2](#)). All study data will be recorded in the subject's source documentation and then on the appropriate eCRFs, with the exception of central laboratory data which will be provided to AbbVie electronically from the individual laboratory(ies).

Informed Consent and RBV Information

Signed study-specific informed consent will be obtained from the subject before any study procedures are performed. Subjects on a RBV-inclusive regimen will be given the RBV Medication Guide (where applicable/locally available). Details about how informed consent will be obtained and documented are provided in Section [9.3](#).

Medical History

A complete medical history, including history of tobacco and alcohol, will be taken from each subject during the Screening Visit. The subject's medical history will be updated at the Study Day 1 Visit. This updated medical history will serve as the baseline for clinical assessment.

Physical Examination

A complete physical examination will be performed at visits specified in [Table 4](#) or upon subject discontinuation. A symptom-directed physical examination may be performed at any other visit, when necessary.

The physical examination performed on Study Day 1 will serve as the baseline physical examination for clinical assessment. Any significant physical examination findings after the first dose will be recorded as adverse events.

Vital Signs, Weight, Height

Body temperature (oral or tympanic), blood pressure, pulse, and body weight will be measured at the visits indicated in [Table 4](#) and [Table 5](#). Blood pressure and pulse rate will be measured after the subject has been sitting for at least 3 minutes. The subject should wear lightweight clothing and no shoes during weighing. Height will only be measured at Screening; the subject will not wear shoes.

12-Lead Electrocardiogram

A 12-lead resting ECG will be obtained at visits specified in [Table 4](#) (or as clinically needed). The ECG will be obtained prior to the blood collection.

ECGs will be recorded after the subject has been supine for at least 5 minutes. Subjects should be instructed to remain completely stationary during the ECG recording (approximately 10 seconds), with no talking, laughing, deep breathing, sleeping, or swallowing.

The ECGs will be evaluated by an appropriately trained physician at the site ("local reader"). The local reader from the site will interpret, sign, and date all ECG tracings and will provide his/her global interpretation as a written commitment on the tracing using the following categories:

- Normal ECG
- Abnormal ECG – not clinically significant
- Abnormal ECG – clinically significant

Only the local reader's evaluation of the ECG will be collected and documented in the subject's source. The automatic machine reading (i.e., machine-generated measurements

and interpretation that are automatically printed on the ECG tracing) will not be collected. The QT interval measurement (corrected by Fridericia's formula, QTcF) will be documented in the eCRF only if the local reader selects "prolonged QT" on the eCRF.

The original ECG tracing will be retained in the subject's record at the study site.

Clinical Laboratory Tests

Samples will be obtained at a minimum for the clinical laboratory tests outlined in [Table 6](#) at the visits specified in [Table 4](#) and [Table 5](#). Blood samples for serum chemistry tests should ideally be collected following a minimum 8-hour fast (with the exception of the Screening Visit, which may be done non-fasting). Subjects whose visits occur prior to the morning dose of study drugs should be instructed to fast after midnight. Subjects whose visits occur following the morning dose of study drugs should be instructed to fast after breakfast until the study visit occurs. Blood samples should still be drawn if the subject did not fast for at least 8 hours. Fasting status will be recorded in the source documents and on the laboratory requisition. The baseline laboratory test results for clinical assessment for a particular test will be defined as the last measurement prior to the initial dose of study drugs.

A central laboratory will be utilized to process and provide results for the clinical laboratory tests.

Sites should refer to the laboratory manual provided by the central laboratory, AbbVie, or its designee for instructions regarding the collection, processing, and shipping of all laboratory samples.

The certified laboratory chosen for this study is Covance. Depending on the location of the study site, samples will be sent to one of the following addresses:

Ombitasvir/ABT-450/Ritonavir
M14-567 Protocol
EudraCT 2014-003147-35

For sites in the Canada and USA:

Covance
[name]
[name]

For sites in the United Kingdom:

Covance
[name]
[name]
[name]

For sites in Australia and New Zealand:

Covance (Asia) Pte Ltd.
[name]
[name]
[name]

Table 6. Clinical Laboratory Tests

Hematology	Clinical Chemistry	Urinalysis
Hematocrit	Blood Urea Nitrogen (BUN)	Specific gravity
Hemoglobin	Creatinine	Ketones
Red Blood Cell (RBC) count	Total bilirubin ^a	pH
White Blood Cell (WBC) count	Direct and indirect bilirubin	Protein
Neutrophils	Serum glutamic-pyruvic transaminase (SGPT/ALT)	Blood Glucose
Bands Lymphocytes Monocytes	Serum glutamic-oxaloacetic transaminase (SGOT/AST)	Urobilinogen
Basophils	Alkaline phosphatase	Bilirubin
Eosinophils	Sodium Potassium Calcium	Leukocyte esterase
Platelet count (estimate not acceptable)	Inorganic phosphorus	Microscopic (reflex)
ANC	Uric acid	Albumin
Prothrombin Time/INR	Cholesterol	Additional Tests
Activated partial thromboplastin time (aPTT)	Total protein	HBsAg
Reticulocyte count	Glucose	Anti-HCV Ab ^c
	Triglycerides	Anti-HIV Ab ^c
	Albumin	FSH (females) ^c
	Chloride	Urine and Serum Human Chorionic Gonadotropin (hCG) (females) ^d
	Bicarbonate	Total insulin
	Magnesium	HCV RNA Hemoglobin A1C ^c
	Gamma-glutamyl transferase (GGT) ^a	IP-10
	Creatinine clearance (Cockcroft-Gault calculation)	IL28B ^c
	Alpha2-macroglobulin ^{a,b}	HCV genotype and subtype ^c
	Haptoglobin ^{a,b}	Pharmacogenetic sample (optional)
	Apolipoprotein A1 ^{a,b}	mRNA sample (optional)

- a. Component of FibroTest.
- b. Performed only during Screening Period for FibroTest, if needed.
- c. Performed only at Screening.
- d. Urine pregnancy testing is not required after Day 1 for female subjects who are confirmed to be post-menopausal or who have a documented history of prior bilateral tubal ligation, bilateral oophorectomy or hysterectomy.

For any laboratory test value outside the reference range that the investigator considers clinically significant:

- The investigator will repeat the test to verify the out-of-range value.
- The investigator will follow the out-of-range value to a satisfactory clinical resolution.

- A laboratory test value that requires a subject to be discontinued from the study or study drugs or requires a subject to receive treatment that will be recorded as an adverse event.

The management of laboratory abnormalities that may occur during the study is described in Section [6.7](#).

Pregnancy Test

A urine pregnancy test will be performed for all female subjects at all visits specified in [Table 4](#) and [Table 5](#). In addition, a serum pregnancy test will be performed at Screening and Study Day 1 Visits and analyzed by the central laboratory. All urine pregnancy tests will be performed on-site during the study visit if there is a scheduled visit, as specified in [Table 4](#) and [Table 5](#). A positive urine pregnancy test requires a confirmatory serum test. Urine pregnancy tests are not required after Day 1 for female subjects with a documented history of bilateral tubal ligation, bilateral oophorectomy, hysterectomy, or for subjects who are confirmed to be postmenopausal. Confirmation of postmenopausal status will be determined during the Screening period, based on the subject's history, and measured by FSH.

For subjects on a RBV-inclusive regimen where there is not a scheduled study visit, female subjects of childbearing potential may either have PT Period pregnancy testing performed at the site as an unscheduled visit using an unscheduled visit test kit or a urine pregnancy test may be conducted by the subject at home with a pregnancy test kit provided by the site; site personnel should contact these female subjects to capture the results of any study-related pregnancy tests performed at home. The pregnancy test results will only be recorded in the subject's source records.

If the subject elects to return to the study site for an unscheduled visit for pregnancy testing, the results of the urine pregnancy test will be recorded on the eCRF, unless serum pregnancy test is elected. Serum pregnancy testing will be completed by the central laboratory and loaded into the clinical database.

Hepatitis and HIV Screen

HBsAg, anti-HCV Ab, and anti-HIV Ab will be performed at Screening. The investigator must discuss any local reporting requirements to local health agencies with the subject. The site will report these results per local regulations, if necessary. The HBV HBsAg results will be reported by the central laboratory to the clinical database.

HCV Genotype and Subtype

Plasma samples for HCV genotype and subtype will be collected at Screening. Genotype will be assessed using the Versant® HCV Genotype Inno-LiPA Assay, version 2.0 or higher (LiPA; Siemens Healthcare Diagnostics, Tarrytown, NY).

Liver Diagnostic Testing

FibroTest/APRI and FibroScan are non-invasive measurements of liver fibrosis that have shown good correlation with liver biopsy on predicting the presence of significant fibrosis or cirrhosis.

The identification of cirrhosis on an appropriately performed and reported liver biopsy at any prior time point is considered sufficient and definitive evidence to establish the presence of cirrhosis.

Subjects who have not had a liver biopsy within previous 24 months and who have not a biopsy establishing cirrhosis at any time prior to 24 months but who otherwise meet all of the inclusion criteria and none of exclusion criteria will undergo liver biopsy or **one** non-invasive test (FibroTest/APRI or FibroScan) prior to enrollment. Selection of whether liver biopsy or one of the non-invasive tests should be performed will be based on local standard practice.

For subjects with a FibroScan result that is ≥ 12.5 kPa and < 14.6 kPa; **or** a FibroTest result that is ≤ 0.72 and an APRI > 2 ; **or** a FibroTest result that is ≥ 0.73 and an APRI ≤ 2 , the subject must have a liver biopsy performed within 24 months prior to screening, or in

the absence of an available biopsy result within 24 months of Screening, may undergo a liver biopsy during Screening to rule out cirrhosis.

Patient Reported Outcomes (PRO) Instruments (Questionnaires)

Subjects will complete the self-administered PRO instruments (where allowed per local regulatory guidelines) on the study days specified in **Table 4** and **Table 5**. Subjects will be instructed to follow the instructions provided with each instrument and to provide the best possible response to each item. Site personnel shall not provide interpretation or assistance to subjects other than encouragement to complete the tasks. Subjects who are functionally unable to read any of the instruments may have site personnel read the questionnaires to them. Site personnel will encourage completion of each instrument at all visits and will ensure that a response is entered for all items.

In this study, PRO instruments should be consistently presented so that subjects complete the EQ-5D-5L first and then the FSS. PRO instruments should be completed prior to drug administration on Day 1 and prior to any discussion of adverse events or any review of laboratory findings, including HCV RNA levels.

EuroQol-5Dimensions-5 Level (EQ-5D-5L)

The EQ-5D-5L is a health state utility instrument that evaluates preference for health status (utility). The 5 items in the EQ-5D-5L comprise 5 dimensions (mobility, self-care, usual activities, pain/discomfort, and anxiety/depression) each of which are rated on 5 levels of severity. Responses to the 5 items encode a discrete health state which is mapped to a preference (utility) specific for different societies. Subjects also rate their perception of their overall health on a separate visual analogue scale (VAS). The EQ-5D-5L should require approximately 5 minutes to complete.

Fatigue Severity Scale (FSS) Instrument

The FSS measures the impact of fatigue over the past week on specific types of functioning (e.g., motivation, exercise, physical functioning, carrying out duties, interfering with work, family, or social life). The survey consists of 9 questions using a

7-point Likert scale. A total score is calculated as the average of the individual item responses. The scale's psychometric properties have been confirmed in chronic hepatitis C and other diseases. Subjects also rate their perception of their fatigue on a separate visual analogue fatigue scale (VAFS). The FSS should require approximately 5 minutes to complete.

Randomization and Assignment of Subject Numbers

All screening activities must be completed and reviewed prior to subject randomization. Screening numbers will be unique 4-digit numbers and will begin with 1001, with the first two digits representing the investigative site and the last two digits representing the subjects at the site. Enrolled subjects will keep their screening number as their subject number. Subjects who meet the eligibility criteria may proceed to randomization via the IRT system at the Study Day 1 Visit.

Randomized subjects will keep their screening number as their subject number. Subjects will be randomized on Day 1 as described in Section [5.5.3](#) and will receive a separate unique randomization number that will be recorded automatically in the eCRF through the IRT system. The randomization number will be used only by the Sponsor for loading the treatment schedule into the database.

HCV RNA Samples

Plasma samples for HCV RNA levels will be collected as indicated in [Table 4](#) and [Table 5](#). Plasma HCV RNA levels will be determined for each sample collected by the central laboratory using the Roche COBAS TaqMan® real-time reverse transcriptase-PCR (RT-PCR) assay v. 2.0. The lower limit of detection (LLOD) is 20 IU/mL and results below LLOD are reported as "HCV RNA not detected;" the LLOQ for this assay is 25 IU/mL and results below LLOQ, but detectable are reported as "< 25 IU/mL HCV RNA detected."

HCV Resistance Testing Sample

A plasma sample for HCV resistance testing will be collected at the study visits indicated in [Table 4](#) and [Table 5](#).

Specific instructions for preparation and storage of these samples will be provided by the central laboratory, AbbVie, or its designee.

Archive Plasma and Serum Sample

Archive plasma and serum samples will be collected at the study visits indicated in [Table 4](#) and [Table 5](#). Archive plasma and serum samples are being collected for possible additional analyses, including but not limited to, study drug or metabolite measurements, viral load, safety/efficacy assessments, HCV gene sequencing, HCV resistance testing, and other possible predictors of response, as determined by AbbVie.

Specific instructions for preparation and storage of archive samples will be provided by the central laboratory, AbbVie, or its designee.

Interferon Gamma-Induced Protein 10 (IP-10) Levels

A plasma sample for IP-10 testing will be collected at the study visits indicated in [Table 4](#) and [Table 5](#). The IP-10 testing is exploratory and may not be provided to the investigator.

5.3.1.2 Meal and Dietary Requirements

All study drugs should be dosed together and administered with food, i.e., the AM dose of ombitasvir/ABT-450/r and SOF and, if applicable, RBV should be taken together with food and, if applicable, the PM dose of RBV should be taken together with food.

It is recommended that subjects avoid consumption of alcohol within the 72-hour period prior to any study drug administration and throughout the duration of the study.

5.3.1.3 Blood Samples for Pharmacogenetic Analysis

IL28B Samples

One (required) 2 mL whole blood sample for Deoxyribonucleic acid (DNA) isolation will be collected from each subject at Screening for Interleukin 28B (IL28B) pharmacogenetic analysis. The sample will not be used for any testing other than IL28B genotypes. IL28B genotyping will be performed by the central laboratory.

Blood Samples for Pharmacogenetic Analysis (Optional)

One 4 mL whole blood sample for DNA isolation will be collected on Day 1 from each subject who consents to provide a sample for pharmacogenetic analysis. The procedure for obtaining and documenting informed consent is discussed in Section 9.3. If the sample is not collected on Day 1, it may be collected at any time throughout the study.

The sample collection tubes will minimally be labeled with "PG-DNA," protocol number, and subject number. Samples will be shipped frozen to AbbVie or a designated laboratory for DNA extraction and long-term storage. Instructions for the preparation and shipment of pharmacogenetic samples will be provided in the lab manual.

AbbVie will store the DNA samples in a secure storage space with adequate measures to protect confidentiality. The samples will be retained while research on ABT-450/ombitasvir (or drugs of this class) continues but no longer than 20 years.

Blood Samples for Messenger RNA (mRNA) Analysis (Optional)

Separate optional whole blood samples will be collected from those subjects who choose to participate and consent to additional mRNA analysis. The procedure for obtaining and documenting informed consent for this optional sample is discussed in Section 9.3.

Subjects who consent to participate in the mRNA substudy will have blood samples taken as indicated in [Table 4](#) and [Table 5](#).

Messenger RNA levels related to HCV disease or response to drug therapy will be measured in peripheral whole blood. For biomarker analysis, mRNA expression may be analyzed using microarray and polymerase chain reaction (PCR) technique in peripheral blood samples. This analysis will measure the levels of essentially all mRNAs present in the collected peripheral blood samples.

Results of mRNA testing are considered exploratory and may not be included in the Clinical Study Report.

The optional blood samples for mRNA must be collected at visits specified in [Table 4](#) and [Table 5](#). Samples will be shipped frozen to AbbVie or a designated laboratory for RNA extraction and long-term storage.

Samples will be stored in a secure storage space with adequate measures to protect confidentiality. These samples will be retained while research on ombitasvir and ABT-450 or drugs of these classes continues, but no longer than 20 years.

5.3.2 Drug Concentration Measurements

5.3.2.1 Collection of Samples for Analysis

Blood samples for assay of ombitasvir, possible ombitasvir metabolites, ABT-450, possible ABT-450 metabolites, ritonavir, SOF, GS-331007 (predominant circulating metabolite of SOF), and RBV (if applicable) will be collected by venipuncture at each study visit specified in [Table 4](#) (irrespective of study drug dosing time). Actual times of dosing for the last dose and second to the last dose will be recorded on the applicable requisition forms and in the eCFR, and accordingly, time after dose for pharmacokinetic sample collection will be determined.

Intensive pharmacokinetic samples will be collected on Day 1 at 2, 4, and 6 hours post-DAA dose and at the 2-week visit at predose and approximately 2, 4, and 6 hours post-DAA dose. The time that each blood sample is collected will be recorded to the nearest minute on the subject dosing card and in the eCRF.

At each planned collection time, two blood samples will be collected (one 4 mL sample intended for DAA/RBV analysis and one 4 mL sample intended for SOF/GS-331007 analysis).

Approximately 12 DAA/RBV and 12 SOF/GS-331007 blood samples are planned to be collected per subject during 12 weeks of treatment for pharmacokinetic analysis. At minimum, the total number of samples planned for pharmacokinetic analysis is 480 for the entire study.

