The following resistance information will be provided for all subjects: the amino acid variants at baseline at signature resistance-associated positions identified by population nucleotide sequencing and comparison to the appropriate prototypic reference sequence.

The following resistance information will be analyzed for subjects who do not achieve SVR₁₂ and who have a post-baseline sample with HCV RNA \geq 1000 IU/mL: 1) the amino acid variants in available post-baseline samples identified by population and/or clonal nucleotide sequencing and comparison to the baseline sequence, 2) the amino acid variants in available post-baseline samples at signature resistance-associated positions identified by population nucleotide sequencing and comparison to the appropriate prototypic reference sequence, and 3) the persistence of resistance-associated amino acid variants by population and/or clonal nucleotide sequencing during the post-treatment period.

Pharmacokinetic:

Individual plasma concentrations of ABT-450, ritonavir, ombitasvir, SOF, GS-331007, and ribavirin will be tabulated and summarized. Individual plasma concentrations of possible metabolites of ABT-450, ombitasvir, and SOF (other than GS-331007) may be tabulated and summarized if measured and sufficient levels of metabolites are observed.

Values for the pharmacokinetic parameters of ombitasvir, ABT-450, ritonavir, SOF, GS-331007, and RBV (if applicable) including the C_{max} , T_{max} , C_{trough} , and AUC will be determined by noncompartmental methods using intensive pharmacokinetic blood sampling data in the study. Additional parameters or summaries may be determined if useful in the interpretation of the data.

Safety:

The number and percentage of subjects reporting treatment-emergent adverse events will be tabulated by Medical Dictionary for Regulatory Activities (MedDRA) system organ class and preferred term for each treatment arm and overall. Tabulations by treatment arm will also be provided in which the number of subjects reporting a treatment emergent adverse event (MedDRA preferred term) is presented by severity (mild, moderate, or severe) and relationship to study drugs.

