Sofosbuvir is a nucleotide analog NS5B polymerase inhibitor indicated for the treatment of chronic hepatitis C infection as a component of a combination antiviral treatment regimen. The approved dose is 400 mg orally once daily, without regard to food.¹⁶ Sofosbuvir has demonstrated potent activity when administered to HCV genotype 3-infected subjects in combination with RBV.

After oral administration, sofosbuvir is rapidly converted to the predominant circulating metabolite GS-331007 that accounts for greater than 90% of drug related material system exposure, while sofosbuvir accounts for approximately 4% of drug related material. Sofosbuvir peak plasma concentrations occurred 0.5 to 2 hours post-dose and GS-331007 peak plasma concentrations were reached 2 to 4 hours post dose.¹⁶

Sofosbuvir is a substrate of drug transporters P-gp and breast cancer resistance protein (BCRP), while GS-331007 is not. Co-administration of sofosbuvir with drugs that are P-gp inducers in the intestines may decrease sofosbuvir plasma concentrations leading to reduced effect and are not recommended for co-administration with sofosbuvir. Drugs that inhibit P-gp and BCRP may increase sofosbuvir plasma concentrations without increasing GS-331007 plasma concentrations; thus, no precautions in co-administration are warranted. Sofosbuvir and GS-331007 are not inhibitors of P-gp and BCRP.¹⁶

Sofosbuvir is a prodrug extensively metabolized in the liver to the pharmacologically active nucleoside analog triphosphate, GS-461203. Dephosphorylation results in the formation of nucleoside metabolite GS-331007 that cannot be efficiently rephosphorylated and lacks anti-HCV activity in vitro.¹⁶

The majority of the sofosbuvir dose recovered in urine was GS-331007 while 3.5% was recovered as sofosbuvir, suggesting that renal clearance is the major elimination pathway

for GS-331007. The median terminal half-lives of sofosbuvir and GS-331007 were 0.4 and 27 hours, respectively.¹⁶

Sofosbuvir was well tolerated in clinical trials, with $\leq 1.5\%$ of subjects discontinuing therapy with SOF + RBV or SOF + pegIFN + RBV for 12 weeks. The most frequently reported adverse events were typically mild to moderate and included fatigue, nausea, and headache.

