5.3.6 Pharmacokinetic Variables

Plasma samples for ombitasvir, ABT-450, ritonavir, SOF, GS-331007 (predominant circulating metabolite of SOF), and RBV (if applicable) will be collected at each study visit up to 12 weeks. Individual plasma concentrations of possible metabolites of ombitasvir and ABT-450 may be measured and summarized if they are needed for additional safety or efficacy evaluation.

Values for the pharmacokinetic parameters of ombitasvir, ABT-450, ritonavir, SOF, GS-331007 (predominant circulating metabolite of SOF), and RBV (if applicable) including the C_{max} , T_{max} , C_{trough} , and AUC will be determined by noncompartmental methods using intensive pharmacokinetic blood sampling data in the study. Additional parameters or summaries may be determined if useful in the interpretation of the data.

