8.1.6 Pharmacokinetic and Exposure-Response Analyses

Individual plasma concentrations of ABT-450, ritonavir, ombitasvir, SOF, GS-581007, and RBV will be tabulated and summarized. Individual plasma concentrations of possible

metabolites of ABT-450, ombitasvir, and SOF (other than GS-331007) may be tabulated and summarized if measured and sufficient levels of metabolites are observed.

Values for the pharmacokinetic parameters of ABT-450, ombitasvir, ritonavir, SOF, GS-331007, and RBV including the C_{\max} , T_{\max} , C_{trough} , and AUC will be summarized and tabulated. Plasma concentration data from this study may be combined with data from other studies and analyzed using the following general methodology. Population pharmacokinetic analyses will be performed using a nonlinear mixed-effects modeling (NONMEM) software (Version VI or higher). The structure of the starting pharmacokinetic model will be based on the pharmacokinetic analysis of data from previous studies. Apparent oral clearance (CL/F) and apparent volume of distribution (V/F) of the PK analytes will be the pharmacokinetic parameters of interest in the analysis. If the estimation of the parameters describing absorption characteristics is not possible then they will be fixed to the values obtained from previous analysis. The evaluation criteria described below will be used to examine the performance of different models.

- Model discrimination will be assessed by a likelihood ratio test comparing objective function values (OFVs) when two competing models are compared. An OFV difference (ΔOFV) of 3.84 will be considered to be significant (χ^2 , $p < 0.05$) when two nested models with a difference of one parameter ($df = 1$) are compared. The Akaike's information criterion (AIC) will be used to compare non-nested models.
- Various goodness-of-fit criteria, including diagnostic scatter plots and individual plots of model fits.
- Visual predictive checks or standardized visual predictive checks.
- Plausibility of parameter estimates and precision of parameter estimates.

Covariate-parameter relationships will be tested based on scientific principles or prior knowledge i.e., only physiologically relevant or clinically meaningful covariates (such as subject age, sex, body weight, concomitant medications, laboratory markers of hepatic or renal function, etc.) will be explored. Covariate modeling will also be guided by plots of

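### Noncompartmental Cmax, Tmax and AUC are planned for parent sofosbuvir from post-dose draws that begin at 2 h, the far end of the protocol's own 0.5 to 2 h peak range

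*Protocol*

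**What the plan says.** Protocol Section 5.3.2.1 sets the intensive sampling: "Intensive pharmacokinetic samples will be collected on Day 1 at 2, 4, and 6 hours post-DAA dose and at the 2-week visit at predose", followed at that visit by draws at about 2, 4 and 6 h after the dose. Table 4, footnote m, gives the same times. The remaining draws are one per visit and are not timed to the dose.

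The synopsis lists the analytes and parameters: "Values for the pharmacokinetic parameters of ombitasvir, ABT-450, ritonavir, SOF, GS-331007, and RBV (if applicable) including the" Cmax, Tmax, Ctrough and AUC. Section 5.3.6 has the same list and says the values "will be determined by noncompartmental methods using intensive pharmacokinetic blood sampling data in the study". Section 8.1.6 plans to tabulate them: "Values for the pharmacokinetic parameters of ABT-450, ombitasvir, ritonavir, SOF, GS-331007, and RBV including the" same four parameters. In all three places parent sofosbuvir is listed separately from its metabolite GS-331007.

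On the parent drug's kinetics, Section 3.0 says "Sofosbuvir peak plasma concentrations occurred 0.5 to 2 hours post-dose" and "The median terminal half-lives of sofosbuvir and GS-331007 were 0.4 and 27 hours, respectively". It puts the GS-331007 peak at 2 to 4 h.

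**The concern.** The first post-dose sample falls at the latest time at which Section 3.0 expects the parent drug to peak. With a half-life of 0.4 h, a subject who peaks earlier has lost much of the peak by then, and nothing is measured in between. The tabulated Tmax would then mostly restate the draw schedule. Cmax would depend on how long before the first draw each subject peaked, and AUC on a stretch of curve that nobody observed.

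Sofosbuvir pharmacokinetics is named in the secondary objectives (Section 4.2), and Section 5.6.1 says the study will inform on it with and without ribavirin. A reader of the report could take the parent-drug table as a description of the drug in these subjects.

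**Working it through.** **1. Is there an earlier draw hidden in the schedule?** Section 5.3.2.1 states about 12 samples of each type per subject and at least 480 in all. Counting from Table 4: Day 1 (3) + Week 1 (1) + Week 2 (4) + Weeks 4, 8, 10 and 12 (1 each) = 12. Two tubes each and 20 subjects give 12 × 2 × 20 = 480. The stated figure reproduces, so no earlier intensive draw is left uncounted.

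**2. Parent level at 2 h.** Inputs from Section 3.0: true Tmax 0.5 to 2 h, half-life 0.4 h. Assumption: simple exponential decline after the peak. The share of the peak left at time t is 0.5^((t − Tmax)/0.4).

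| True Tmax (h) | Half-lives to 2 h | Left at 2 h | Left at 4 h |
|---|---|---|---|
| 0.5 | 3.75 | 7.4% | 0.23% |
| 1.0 | 2.50 | 17.7% | 0.55% |
| 1.5 | 1.25 | 42.0% | 1.3% |
| 2.0 | 0 | 100% | 3.1% |

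The 2 h sample is the highest in every row, so it supplies both observed Cmax and observed Tmax.

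**3. AUC.** The documents give no profile shape and no trapezoid rule, so this step is illustrative. Assume a linear rise from zero to a peak of 1 at Tmax, then decline at k = ln 2/0.4 = 1.733 per h.

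- True AUC = Tmax/2 + 1/k = Tmax/2 + 0.577.
- The linear trapezoid on 0, 2, 4 and 6 h, with zero at time 0, gives 2·C2 + 2·C4 + C6. Since C4 = C2/32 and C6 = C2/1024, this is 2.0635 × C2.

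| True Tmax (h) | Trapezoid | True | Ratio | Share of true AUC before 2 h |
|---|---|---|---|---|
| 0.5 | 0.153 | 0.827 | 0.19 | 95% |
| 1.0 | 0.365 | 1.077 | 0.34 | 90% |
| 1.5 | 0.868 | 1.327 | 0.65 | 82% |
| 2.0 | 2.064 | 1.577 | 1.31 | 63% |

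The result moves with the assumptions. On the same profile, a linear-up/log-down rule gives 0.14, 0.26, 0.50 and 1.00. First-order absorption with a rate of 2.29 per h, lagged where Tmax exceeds 0.5 h, gives 0.31 to 1.60 by linear trapezoid.

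**4. Ctrough.** This comes from the Week 2 pre-dose draw, about 24 h after the previous dose. That is (24 − 2)/0.4 = 55 to (24 − 0.5)/0.4 = 58.75 half-lives after the peak.

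**5. GS-331007, for contrast.** With a peak at 2 to 4 h and a half-life of 27 h, 0.5^(4/27) = 90% to 0.5^(2/27) = 95% of the peak remains at 6 h. At 24 h, 0.5^(22/27) = 57% to 0.5^(20/27) = 60% remains. The draws cover its peak and trough. AUC over the full dosing interval would still need interpolation between 6 h and the trough; that is not examined here.

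**The case against.** **The kinetics may not be those of this trial.** Section 3.0 takes its figures from the product label. Here sofosbuvir is taken with food (Section 5.3.1.2) and alongside ritonavir. A later peak would reduce the Cmax and Tmax error, and a peak at 2 h is caught. This stands as a condition on the finding. The documents give no fed or co-dosed figures, so they do not remove it either.

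**Ctrough.** A reader might infer that all four parameters are spoiled by the 2 h start. They are not: Ctrough has its own pre-dose draw. Its value is effectively zero and so uninformative, but not biased.

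**Size of the AUC error.** A reader might also infer an overstatement approaching threefold. A ratio of 2.85 can be produced at a true Tmax of 2 h, but only with an absorption rate of 20 per h after a lag of about 1.87 h. Nothing in the documents supports that lag or rate.

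**Modelling can fill the gap.** Section 8.1.6 describes population modelling, but "Plasma concentration data from this study may be combined with data from other studies" makes pooling optional, and absorption parameters that cannot be estimated are fixed to earlier values. This can help, but it does not replace the noncompartmental commitment.

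**Little depends on it.** Section 3.0 says "sofosbuvir accounts for approximately 4% of drug related material". Dosing waits for the interaction results of Study M14-527 (Sections 3.2 and 5.6.1), one schedule serves six analytes, and no decision rule uses the parent parameters. All of this stands and sets the severity.

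**The text may be superseded.** The protocol reviewed is the two-arm version with about 20 subjects. The SAP describes six arms and about 70 subjects, and its Section 12.1 refers to a latest protocol version. Later sampling text may exist. The SAP has no pharmacokinetic analysis section, but its stated scope is the work of Statistics and Statistical Programming, so that absence is not counted as an error.

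**Conclusion.** The point holds for parent sofosbuvir Cmax, Tmax and AUC, on the condition that the Section 3.0 kinetics apply with food and ritonavir. Observed Tmax is then about 2 h or later in essentially every subject. Observed Cmax runs from about 7% of the true value (Tmax 0.5 h) to 100% (Tmax 2 h); these figures need only the stated peak range and half-life plus exponential decline. The AUC figure of about 0.19 to 1.31 times true also needs a linear rise and a linear trapezoid. What carries over to other shapes is that AUC depends on an unmeasured interval. Because its error varies with a Tmax the design cannot observe, no correction factor can repair it.

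The documents do not support reading this as a failure of the pharmacokinetic objective as a whole. Severity is minor: one analyte of a secondary objective is affected, and SVR12, safety and sample size are not.

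**What to change.** In the synopsis and Sections 5.3.6 and 8.1.6, take parent sofosbuvir out of the list of noncompartmental Cmax, Tmax, Ctrough and AUC, and keep GS-331007 in it. Report parent sofosbuvir concentrations by actual time after dose; the concentrations are already to be tabulated and the sampling times recorded to the minute. Give model-based parent estimates only where pooled data from other studies cover the first 2 h, and state any absorption parameter that was fixed to an earlier value.

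The cost is wording in three places, with no change to visits or draws. The sponsor loses a descriptive parent-drug parameter table. If a later protocol version already has earlier sofosbuvir draws, no change is needed.
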